7.1. ADVERSE EVENTS DEFINITIONS

Standard definitions for AEs are provided in this section for informational purposes.

7.1.1. Adverse Event (21 CFR 312.32(a))

AE means any untoward medical occurrence associated with the use of a drug in humans, whether or not considered drug related. An AE can be any unfavorable and unintended sign (e.g., an abnormal laboratory finding), symptom, or disease temporally associated with the use of a drug, without any judgment about causality.

Within this investigation, adverse events also encompass procedurally related observations based upon physical examination of the patient, or laboratory assessments or spontaneously reported by the subject which are temporally associated with the administration of study medication.

For adverse events requiring medical interventions such as surgeries, diagnostic procedures and therapeutic procedures it is recommended that these be recorded as treatment of the adverse event or action taken rather than an additional adverse event.

Brainstorm Cell Therapeutics Ltd. Phase 2 Clinical Protocol BCT-101-US Amendment 1.1, June 2019	IND#018615 MSC-NTF cells (NurOwn®)	Page 37 of 59
---	---------------------------------------	---------------

7.1.2. *Serious Adverse Event (21 CFR 312.32(a))*

An AE or suspected adverse reaction is considered “serious” (SAE) if, in the view of either the Investigator or Sponsor, it results in any of the following outcomes:

- Death
- Life-threatening (an AE or suspected adverse reaction is considered “life-threatening” if, in the view of either the Investigator or Sponsor, its occurrence places the subject or subject at immediate risk of death. It does not include an AE or suspected adverse reaction that, had it occurred in a more severe form, might have caused death)
- Inpatient hospitalization or prolongation of existing hospitalization excluding:
 - A visit to the emergency room or other hospital department for <24 hours that does not result in admission (unless considered an important medical event or life-threatening)
 - An elective surgery planned prior to signing informed consent
 - Protocol specified admissions for planned procedures
 - Admission for social circumstance that has no bearing on health status and requires no intervention (e.g., economic inadequacy, family circumstances, administrative)
- A persistent or significant incapacity or substantial disruption of the ability to conduct normal life functions
- A congenital anomaly/birth defect
- Important medical events that may not result in death, be life-threatening, or require hospitalization may require medical or surgical intervention to prevent one of the outcomes listed in this definition. Examples of such medical events include allergic bronchospasm requiring intensive treatment in an emergency room or at home, blood dyscrasias or convulsions that do not result in inpatient hospitalization, or the development of drug dependency or drug abuse.

If it is not certain that an event meets the above definitions of an SAE, the site Investigators will contact the Medical Monitor to discuss.

7.1.3. *Relatedness (Causality)*

Investigators will assess relatedness of AEs to study drug using the following terms:

- **Definite:** An AE that has a clear temporal association with investigational product administration (e.g., within 72 hours); provides a plausible pharmacologic explanation for the event
- **Probable:** There is a reasonable temporal association with administration of the investigational product; unlikely caused by other drugs or underlying conditions
- **Possible:** There is a plausible temporal association with the investigational product, but other etiologies are possible and relatedness to the investigational product cannot definitely be ruled out

Brainstorm Cell Therapeutics Ltd.	IND#018615	
Phase 2 Clinical Protocol BCT-101-US	MSC-NTF cells (NurOwn®)	Page 38 of 59

- **Unlikely:** The temporal association with the investigational product is implausible (but not impossible). The event is likely related to other drugs or conditions
- **Not Related:** An AE with no temporal association with the investigational product but rather related to other etiologies such as concomitant medications or conditions or subject's known clinical state; subject has not received investigational product.

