8. SAFETY AND TOLERABILITY

All safety analyses will be based upon the Safety Population.

All AEs will be coded to SOC and PT using the MedDRA, version 21.1.

A Treatment-emergent adverse event (TEAE), referred to subsequently as just TEAE or AE is an AE that occurs for the first time after initiation of first treatment or if it had occurred prior to initiation first treatment, it worsens in severity after initiation of first treatment.

AE's that occur prior to initiation of first treatment will only be in the listings and not included in any summary Tables.

AE's related to the Bone Marrow Aspiration will be included in a separate listing.

When evaluating changes in continuous safety parameters (such as laboratory measurements, vital signs, ECGs, etc.) , Baseline will be defined as the last measurement prior to first transplantation (i.e., prior to initiation of treatment).

Additional details for analysis of safety data are detailed below.

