8.1. Overall Summary of Tolerability

The overall summary of tolerability table will present data by the NurOwn® group. Entries in this table will include:

1. Number of TEAEs
2. Subjects with at least one
 - a. Adverse event including procedure related AEs
 - b. Procedure related AEs
 - c. AE excluding procedure related AEs
 - d. AE related to the study medication
 - e. Severe AEs including procedure related Severe AEs
 - f. Severe AEs related to procedure
 - g. Severe AEs excluding procedure related Severe AEs
 - h. Severe treatment related AEs
 - i. Serious AEs
 - j. Serious treatment related AEs
 - k. AEs leading to study discontinuation
 - l. MS relapses
 - m. AEs leading to death

The above summaries will include the number of events as well as number and percentage of subjects experiencing at least one TEAE.

The subject data listing provides a complete list of all AEs as recorded in the CRF and supports this table and all other AE summary table subsets.

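### Causality is assessed against study drug only, and its timing conditions keep lumbar-puncture events at 'Possible' or higher, while the SAP reports product-related and procedure-related AEs separately without an attribution rule

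*Protocol*

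**What the plan says.** **Protocol 7.1.3** sets the object of the causality assessment: "Investigators will assess relatedness of AEs to study drug using the following terms". Five terms follow.

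- *Definite* needs clear timing and an event for which the product "provides a plausible pharmacologic explanation for the event".
- The wording of *Probable* is as follows: "There is a reasonable temporal association with administration of the investigational product; unlikely caused by other drugs or underlying conditions".
- The next term, *Possible*, needs plausible timing, "but other etiologies are possible and relatedness to the investigational product cannot definitely be ruled out".
- *Unlikely*: "The temporal association with the investigational product is implausible (but not impossible"), with other drugs or conditions as the likely cause.
- *Not Related* needs the absence of any link in time with the product. It gives an open list of other causes, and also covers a subject who has not been dosed.

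**Protocol 7.1.1** brings procedural observations into the AE definition, namely those "which are temporally associated with the administration of study medication". It does not say how to attribute them. Protocol 9.3.5 plans a summary of treatment-related TEAEs and none of procedure-related ones.

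**SAP 8.1** has a row for AEs related to study medication, a row for procedure-related AEs and a row for "AE excluding procedure related AEs", with a similar set for severe AEs. SAP 8.2.1 repeats the split by SOC and PT. SAP 8 adds: "AE's related to the Bone Marrow Aspiration will be included in a separate listing". **SAP Appendix I, 4.1** drops some tables because too few subjects are involved, naming procedure-related AEs as an example, and moves those subjects to listings.

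**The concern.** Safety and tolerability of three intrathecal doses is the primary objective, and the study is meant to inform a later randomised trial. There is no control arm and no puncture without cells, so investigator attribution is the main planned means of separating product effects from procedure effects. Treatment-relatedness also carries weight as a headline: Protocol 10.1 summarises the earlier studies by the absence of treatment-related SAEs.

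If the scale cannot place a puncture event below *Possible*, the study-medication row will mix the two sources. If the procedure flag has no stated rule, the rows and tables that exclude procedure-related AEs depend on a classification the reader cannot reconstruct. The same event could be counted as related to study medication in one row and removed as procedure-related in another.

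**Working it through.** The plan states no figure for this point. The check is a reading of the scale against the schedule, followed by a count of affected outputs and an illustration.

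**1. Is any planned puncture done without dosing?** Protocol 2.3.2 describes one lumbar puncture per treatment: CSF is drawn and the cells are then injected. Protocol 4.7.1, 4.7.3 and 4.7.5 repeat this for Visits 3, 4 and 5. Table 1 places CSF collection and transplant at those three visits only. So 20 x 3 = up to 60 planned punctures, and 0 without product.

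**2. Which terms can a puncture event receive?** Take an event shortly after dosing that the investigator believes is due entirely to the needle.

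| Term | Timing condition met? | Other condition | Open on a literal reading? |
|---|---|---|---|
| *Definite* | Yes | Pharmacologic explanation | Poor fit for a mechanical injury |
| *Probable* | Yes | Other drugs or underlying conditions unlikely as the cause | Yes; a puncture is neither |
| *Possible* | Yes | Other etiologies possible, product role not definitely ruled out | Yes |
| *Unlikely* | No; timing must be implausible | Likely due to other drugs or conditions | No |
| *Not Related* | No; there must be no link in time | Other etiologies, open list | No |

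The two terms that would say the product was not the cause are closed by timing alone. *Possible* is the lowest term open.

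**3. Which SAP outputs need a procedure flag?** SAP 8.1 lists 13 subject rows (a to m). Rows b, c, f and g either select or exclude procedure-related AEs: 4 of 13. SAP 8.2.1 lists 10 AE categories. Procedure-related AEs, all AEs excluding them, and the two corresponding severity tables need the flag: 4 of 10. These counts describe the April 2019 SAP; Appendix I later moves some of this output to listings.

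**4. Is the rule stated anywhere?** Neither Protocol 7.1, Protocol 9.3.5, SAP 8 nor Appendix I 4.1 defines procedure-related or says who decides it. None states which of the five levels enter the row for AEs related to study medication.

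**5. Illustration only (assumed counts, not data).** Suppose 2 of 20 subjects have a truly product-related AE, 6 others have a puncture headache, and there are no other AEs. Intervals are exact binomial (Clopper-Pearson, 95%).

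- Puncture events kept out of the related row: 2/20 = 10% (1% to 32%).
- Puncture events graded *Possible*, with *Possible* counted as related: (2 + 6)/20 = 8/20 = 40% (19% to 64%).

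With the 6 headaches also flagged as procedure-related, SAP row c (AEs excluding procedure-related) would hold 2 subjects and row d (related to study medication) 8. The related row would exceed the row from which procedural events have been removed.

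**The case against.** The strongest reply is that the scale is more flexible than a quick reading suggests, and much of it stands.

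- A reader might infer that the scale admits only other drugs or conditions as alternative causes. That is true of *Probable* and *Unlikely*. *Possible* and *Not Related* refer to other etiologies in open terms, and a puncture can be one.
- A reader might infer that a post-puncture headache must be at least *Probable*, or that *Definite* is easier still to reach. Neither follows. The headache fits *Possible* closely, and the pharmacologic test in *Definite* works against a mechanical injury.
- A reader might infer that the SAP split has no basis in the protocol. Protocol 7.1.1 does count procedural observations as AEs, and Appendix I implies such events were identified. The eCRF and its completion guidance are not among the documents, so it cannot be shown that the classification was unguided.
- A reader might infer that bone marrow aspiration events are misgraded. Before dosing, *Not Related* to the product is the correct grade. SAP 8 keeps pre-treatment AEs out of all summary tables, so they cannot enter the related rows.
- The primary objective concerns the treatment as delivered, and no attribution scheme in a single-arm study can prove which harm comes from the cells.

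None of this reopens *Unlikely* or *Not Related* for an event that follows a dosing puncture. The open wording in *Not Related* is of no use while its timing condition blocks it. The table of AEs by relationship to study medication (SAP 8.2.1) shows the levels, but *Possible* would still pool doubtful product effects with clear needle effects.

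**Conclusion.** The point holds in a limited form. Relatedness is assessed against study drug only, and the timing conditions in *Unlikely* and *Not Related* push an event due wholly to the puncture to *Possible* or *Probable*. The SAP reports product-related and procedure-related AEs separately, yet neither document gives an attribution rule for procedures or a cut-off for related.

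The scope is up to 60 dosing punctures, 4 of 13 rows in SAP 8.1 and 4 of 10 categories in SAP 8.2.1, less the output Appendix I moves to listings. The effect on reported rates cannot be estimated from the documents; the 10% versus 40% contrast shows only how far the rule could matter under invented counts.

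The conclusion assumes that investigators apply the terms as written and that no unseen eCRF guidance overrides them. Whether *Possible* counts as related is unstated, and that is part of the gap. The change is recommended because the affected output belongs to the primary safety endpoint and the remedy is cheap.

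**What to change.** **Protocol 7.1.3 and the AE eCRF.** Record causality separately for (i) the cell product and (ii) the lumbar puncture/intrathecal procedure. Add a yes/no item for bone marrow aspiration to support the SAP 8 listing. Name study procedures as an alternative cause in *Probable*, *Unlikely* and *Not Related*. Reword *Unlikely* and *Not Related* so they can be chosen when a study procedure is the likely cause despite close timing. Naming procedures without changing the timing conditions would leave puncture events at *Possible* or higher.

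**SAP 8.1.** Define treatment-related as possible or higher for (i) and procedure-related as possible or higher for (ii). Report product only, procedure only and both.

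**If AE data are already collected.** Document how the existing procedure flag was assigned and by whom, and report the same three groups from it.

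**Cost.** Two extra eCRF items per AE and a short SAP definition. Data entry rises slightly, and some events will be attributed to both sources. In a single-arm study the split remains investigator opinion; it makes the attribution traceable but does not prove which harm belongs to the cells.

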7.1.4. Severity (Intensity)

The severity of an AE will be graded on a scale: mild, moderate, severe, as defined below:

- **Mild:** Asymptomatic or mild symptoms, clinical or diagnostic observations only; intervention not indicated
- **Moderate:** Minimal, local or non-invasive intervention indicated; interferes with age-appropriate activities of daily living
- **Severe:** Disabling; unable to carry out age-appropriate activities of daily living
- **Potentially Life-Threatening:** Medical or operative intervention indicated to prevent permanent impairment, persistent disability, or death.

7.1.5. Follow-Up of AEs

After the initial recording of an AE, the Investigator shall proactively follow the subject. Any non-serious AEs that are still on-going at the end of the study shall be reviewed to determine if further follow-up is required. The Investigator will document on the eCRF any/all on-going non-serious AEs that will not be followed further after the subject exits the study. If in doubt, the Investigator shall consult the study Medical Monitor.

All SAEs shall be followed until resolution, until the condition stabilizes, or until the subject is lost to follow-up, or otherwise explained. Once the SAE is resolved, the corresponding AE eCRF page shall be updated. Additionally, any relevant laboratory test reports, consultation reports from other health care professionals, discharge summaries, or other information that has been gathered about the event shall be transmitted to the Sponsor.

The Sponsor may request that the Investigator perform or arrange for the conduct of supplemental measurements and/or evaluations to elucidate as fully as possible the nature and/or causality of any AE.

7.1.6. Outcome

The following terms will be used during this study:

- Fatal
- Not Recovered/not resolved
- Recovering/resolving
- Recovered/resolved
- Recovered/resolved with sequelae
- Unknown

Brainstorm Cell Therapeutics Ltd.	IND#018615	
Phase 2 Clinical Protocol BCT-101-US Amendment 1.1, June 2019	MSC-NTF cells (NurOwn®)	Page 39 of 59

7.1.7. Clinically Significant Laboratory Abnormalities

Any laboratory abnormalities deemed clinically significant by the Investigator shall be reported on the AE eCRF. A clinically significant abnormality is a confirmed abnormality that is changed sufficiently from screening visit so that in the judgment of the Investigator a change in management is warranted. This alteration may include: monitoring the laboratory test further, initiating other diagnostic tests or procedures, changing ongoing treatment, or administering new treatment. Whenever possible, the etiology of the abnormal finding (e.g., anemia) will be recorded on the eCRF. Repeated additional tests and/or other evaluations required to establish the significance and etiology of an abnormal result shall be obtained when clinically indicated.

VP Scientific and Regulatory Affairs	[name]. [contact] Ext. 102 Email: [contact] Brainstorm Cell Therapeutics Ltd.

The Sponsor or designated clinical safety service provider (ProPharma Group.) will report Investigational New Drug (IND) Safety Reports to the FDA and Investigators in accordance with the FDA regulations detailed in the Code of Federal Regulations (CFR) 21CFR312.32 and in accordance with Guidance for Industry and Investigators: Safety Reporting Requirements for INDs and bioavailability (BA)/bioequivalence (BE) Studies, December 2012. The Investigator at each study site is responsible for reporting SAEs to his or her Institutional Review Board (IRB) in accordance with local IRB procedures.

If new sites are added to the study, the Sponsor or designated clinical safety service provider will notify all Investigators at the sites involved in the study in writing of any severe/serious or unexpected AEs when this information is of global importance to subject safety and welfare.

7.3. REPORTING RESPONSIBILITIES AND PROCEDURES FOR PREGNANCIES

Pregnancy occurring in a female subject (and female partners of male subjects) should be reported to the ProPharma Safety Group by completing the Pregnancy Notification Form within 24 hours of becoming aware of the event. Pregnancy outcome information should be forwarded to Sponsor/ Clinical Safety service Provider when available.

Brainstorm Cell Therapeutics Ltd.	IND#018615	
Phase 2 Clinical Protocol BCT-101-US Amendment 1.1, June 2019	MSC-NTF cells (NurOwn®)	Page 41 of 59

Any pregnancies will be followed through delivery or premature termination. If a female subject (or female partner of male subject) becomes pregnant during the study, any complications of that pregnancy such as abortion (spontaneous or induced), premature birth, or congenital abnormality will be captured as SAEs.

Following delivery or termination of pregnancy, the Pregnancy Outcome Form should be completed. Follow-up information regarding the outcome of the pregnancy and any postnatal sequelae in the infant will be required.

7.4. PROSPECTIVE ASSESSMENT OF THE OCCURRENCE OF SUICIDALITY

There is no evidence from animal or previous human studies to suggest that NurOwn® (MSC-NTF cells) transplantation will increase suicidal ideation or attempts; but, because these cells are delivered to the CSF and are active in the central nervous system, we plan to monitor suicidal ideation and behavior carefully during the trial.

Suicidal ideation and behavior will be monitored using the C-SSRS (<http://www.cssrs.columbia.edu>), as per the SOA. All study staff delivering the C-SSRS will be fully trained in its appropriate use and only study staff prepared to appropriately respond to participants exhibiting suicidal ideation or behavior will deliver the scale. The 'Baseline' questionnaire will be given at the Screening/Visit. The 'Since Last Visit' questionnaire will be given at the 28-week visit (Visit 7, See Appendix 3).

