2.4. DURATION OF STUDY

Participants will be screened and eligible participants will be enrolled and will undergo viral safety testing within 7 days of the scheduled Bone Marrow Aspiration (BMA).

Following aspiration, MSC will be isolated, propagated for about 2 weeks and cryopreserved. About 2 weeks prior to each treatment, MSC will be thawed, propagated and induced into MSC-NTF cells. Participants will undergo IT administration of NurOwn® (MSC-NTF cells) on Day 0 (Visit 3), Week 8 (Visit 4) and Week 16 (Visit 5). Following each cell transplantation, participants will be monitored as inpatients for a period of up to 24 hours. Participants will be discharged after up to 24 hours unless a clinical AE(s) occurs and requires continued inpatient monitoring and/or treatment. After the last dose, participants will be followed for approximately 12 weeks for efficacy and safety assessment. Each subject's participation in the study will last for approximately 38 weeks.

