4.6. PRE-TRANSPLANTATION VISITS

4.6.1. Visit 1: Screening Visit

Visit 1 is the Screening Visit and precedes Visit 2 by up to 4 weeks

Participants will undergo the following screening assessments:

- Informed consent (to be obtained by the Principal Investigator [PI] or Sub-Investigator [Sub-I])
- Determine study eligibility, review of Inclusion/Exclusion Criteria
- Collect demographic data
- Medical history
- Medical history of MS symptoms and date of diagnosis
- Standard 12-Lead ECG
- Neurological examination
- Review of prior concomitant medications
- Review of adverse events (AEs)
- Directed physical examination, including height and weight
- Vital sign measurements (including blood pressure, body temperature; pulse and respiration rate after sitting for at least 3 minutes)
- Blood collection for hepatitis B virus (HBV; surface antigen (HBsAg) and antibodies to core antigen (IgG and IgM anti-HBc), hepatitis C virus (HCV), human immune deficiency virus (HIV) 1 and 2. These tests must be performed within 7 days of Bone Marrow aspiration, and must be repeated if Bone Marrow aspiration is scheduled more than 7 days after the

Brainstorm Cell Therapeutics Ltd.	IND#018615	
Phase 2 Clinical Protocol BCT-101-US Amendment 1.1, June 2019	MSC-NTF cells (NurOwn®)	Page 28 of 59

Screening visit. Viral safety tests must be performed by CLIA certified laboratories using Food and Drug Administration (FDA) cleared kits.

- Blood collection for hematology (CBC (hematology panel) - hemoglobin, hematocrit, white count (and differential), platelet count), coagulation (PT, PTT, INR), biochemistry evaluations (Sodium, potassium, chloride, glucose, BUN, creatinine, bicarbonate, calcium, total bilirubin, AST, ALT, ALP, uric acid, total cholesterol, HDL, LDL)
- Blood collection for a serum pregnancy test (Female participants of childbearing potential)
- Urinalysis (Specific gravity, pH, glucose, protein, ketones, blood)
- Columbia-Suicide Severity Rating Scale (C-SSRS baseline)
- MS functional composite (MSFC): T25FW and 9HPT
- EDSS
- MSWS-12
- LCLA
- SDMT
- MRI
- For eligible subjects: issue wearable sensor device and train on timing of use as well as maintenance of device

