4.8.2. Visit 6: Week 22 (\pm 5 days) Follow-Up

At the Week 22 follow-up visit, participants will undergo:

- Review of concomitant medications
- Review of adverse events
- Vital sign measurements (including blood pressure, body temperature; pulse and respiration rate after sitting for at least 3 minutes)
- Directed physical examination
- Blood collection for biomarker analyses
- MS functional composite (MSFC): T25FW and 9HPT
- EDSS
- MSWS-12
- LCLA
- SDMT

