15.3. APPENDIX 3: C-SSRS

Suicidal ideation and behavior is assessed using the Columbia-Suicide Severity Rating Scale (C-SSRS).

The binary responses, yes or no, can be categorized in one of the following:

Category 1 – Wish to be Dead

Category 2 – Non-specific Active Suicidal Thoughts

Category 3 – Active Suicidal Ideation with Any Methods (Not Plan) without Intent to Act

Category 4 – Active Suicidal Ideation with Some Intent to Act, without Specific Plan

Category 5 – Active Suicidal Ideation with Specific Plan and Intent

Category 6 – Preparatory Acts or Behavior

Category 7 – Aborted Attempt

Category 8 – Interrupted Attempt

Category 9 – Actual Attempt (non-fatal)

Category 10 – Suicidal Behavior

Total administration time should be approximately 5 minutes. The suicidal ideation score is the maximum suicidal ideation category (1-5 on the C-SSRS) present at the assessment. If no ideation is present, the suicidal ideation score is 0.

A “yes” answer at any time during treatment to any one of the five suicidal ideation questions (categories 1-5) on the C-SSRS will be categorized as “Suicidal ideation”. A “yes” answer at any time during treatment to any one of the five suicidal behavior questions (categories 6-10) on the C-SSRS will be categorized as “Suicidal behavior”. A “yes” answer at any time during treatment to any one of the ten suicidal ideation and behavior questions (categories 1-10) on the C-SSRS will be categorized as “Suicidal ideation or behavior”.

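### The C-SSRS is scheduled only at screening and Week 28 with an undefined look-back, so continuing participants have no C-SSRS between the first and third doses

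*Protocol*

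**What the plan says.** Protocol 7.4 reports no prior evidence of a raised suicidality risk. Because the cells go into the CSF and act in the CNS, it nevertheless says "we plan to monitor suicidal ideation and behavior carefully during the trial". It names the tool: "Suicidal ideation and behavior will be monitored using the C-SSRS", following the schedule of assessments.

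Two administrations are described. For the first, "The 'Baseline' questionnaire will be given at the Screening/Visit", which the Visit 1 list in 4.6.1 enters as "Columbia-Suicide Severity Rating Scale (C-SSRS baseline". For the second, "The 'Since Last Visit' questionnaire will be given at the 28-week visit (Visit 7, See Appendix 3".

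Protocol Table 1 and SAP Table 2 mark the C-SSRS at Visits 1 and 7 only, and the visit lists in 4.6.1 and 4.8.3 agree. It is absent from the lists for the three transplantation visits (4.7.1, 4.7.3, 4.7.5) and the telephone visits. It is also absent from the Visit 6 list, which opens "At the Week 22 follow-up visit, participants will undergo". Note 11 to Protocol Table 1 adds an Early Termination visit with all Visit 7 procedures, for participants who discontinue after the first treatment.

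On dosing, Protocol 2.4 states: "Participants will undergo IT administration of NurOwn® (MSC-NTF cells) on Day 0 (Visit 3), Week 8 (Visit 4) and Week 16 (Visit 5". Appendix 3 (15.3) classes as suicidal ideation a yes given "at any time during treatment to any one of the five suicidal ideation questions", with parallel rules for behavior and for the two combined. SAP 8.8 plans a listing of C-SSRS data and no table.

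**The concern.** The commitment, the scoring rule and the schedule do not fit together. Section 7.4 is headed as a prospective assessment, and Appendix 3 presumes answers that can be placed within treatment. The schedule gives a continuing participant nothing between a form completed before the bone marrow aspiration and one completed 12 weeks after the third dose (28 − 16 = 12).

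The title of the second form also leaves its look-back open. It may mean the last clinic visit or the last time the scale was given, and no section says which. Sites could apply it differently, and the listing would not show it.

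Two things are at stake. Ideation arising after one dose would not be sought with this instrument before the next. And someone reading a clean Visit 7 entry could not tell whether the dosing period had been asked about. Safety is the primary objective, and this is the only dedicated suicidality measure in the plan.

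**Working it through.** The plan gives no figure to reproduce. The check is date arithmetic on the visit schedule, counting from the first dose as Day 0.

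**Inputs**
- Visit 1: 6 to 10 weeks before first treatment (Synopsis; Protocol Table 1).
- Doses: Day 0, Week 8, Week 16; the Synopsis calls this a 16-week treatment period.
- Third dose: ±14 days (4.7.5). Visit 6: Week 22 ±5 days. Visit 7: Week 28 ±5 days (Protocol Table 1).
- Administration time: about 5 minutes (Appendix 3).

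**Reading A: since the last clinic visit (Visit 6)**
- Look-back = Visit 7 − Visit 6 = 28×7 − 22×7 = 196 − 154 = 42 days.
- Shortest within windows: (196 − 5) − (154 + 5) = 32 days. Longest: (196 + 5) − (154 − 5) = 52 days.
- Share of the time since first dose: 6/28 = 21.4% covered, 22/28 = 78.6% not covered.
- Overlap with Day 0 to Day 112 (Week 16): 0 days.
- Could the windows create an overlap? The latest third dose is 112 + 14 = Day 126 and the earliest Visit 6 is 154 − 5 = Day 149, so the look-back starts at least 149 − 126 = 23 days after the last dose. If the ±14 days in Protocol 2.1 is allowed on each 8-week interval, the third dose could fall at 112 + 28 = Day 140, still 149 − 140 = 9 days before Visit 6.

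**Reading B: since the previous C-SSRS (Visit 1)**
- Look-back = 28 + 6 = 34 weeks to 28 + 10 = 38 weeks.
- Pre-treatment share: 6/34 = 17.6% to 10/38 = 26.3%.
- All three doses fall inside the interval, recalled in one interview.

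**What the Appendix 3 rule can deliver for a participant who completes the study**

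| Visit 7 answer | Reading A | Reading B |
|---|---|---|
| No | Silent on Weeks 0 to 22 | Negative for the treatment period |
| Yes | Event after the last dose, about Weeks 22 to 28 | On or before treatment is unknown unless the event is dated |

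Under both readings, the number of scheduled C-SSRS administrations between the first and third doses is zero.

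**The case against.** The best defence is that 'Since Last Visit' is simply the name of a questionnaire. With only two administrations planned, it is natural to take it as since the previous one. The form's own recall instruction is not in the documents; Appendix 3 gives categories and scoring only. On that reading all dosing is covered, and a no over 34 to 38 weeks is also a no during treatment. This stands. The 21% figure is conditional, and it would be wrong to say that the Appendix 3 classification can never be made.

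Other points also carry weight:
- Adverse events are reviewed at every visit, including the calls 1 to 2 weeks after each dose.
- Serious adverse events go to the DSMB monthly (SAP 5.2).
- Unstable psychiatric disease is an exclusion (Protocol 3.2).
- The Early Termination visit includes the C-SSRS and may fall within the dosing period.
- The C-SSRS is not among the safety endpoints listed in Protocol 9.1.1 or SAP 3.2.1, and no table or rate depends on it.
- The two-visit schedule is stated consistently, so it looks deliberate.

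These reduce the consequence but do not remove the gap. General adverse-event review is not the structured interview by trained staff that 7.4 selects. The Early Termination form does not reach participants who go on to further doses. A listing still needs a known recall period to be interpretable.

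**Conclusion.** The point holds as a mismatch that is cheap to correct. The C-SSRS does not assess continuing participants between the first and third doses, and the Visit 7 look-back is undefined. Its size depends on the reading: either 6 of 28 weeks after first dose and none of the dosing period, or a single 34 to 38 week recall that includes 6 to 10 untreated weeks. The arithmetic assumes visits at their nominal weeks or within the stated windows. Note 12 to Protocol Table 1 allows more flexible timing of transplantation visits.

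A reader might infer three stronger conclusions, and the documents support none of them:
- That the Visit 7 form is settled as covering only Weeks 22 to 28. The text is ambiguous on this.
- That no on-treatment classification is possible. Under the longer recall a no suffices, and a dated yes would too.
- That suicidality during dosing would go unrecorded, or that a planned analysis fails. Adverse-event review runs throughout, and SAP 8.8 plans only a listing.

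**What to change.** Reconcile Protocol 7.4, the two schedules and Appendix 3.

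**At minimum**
- State in 7.4 that the form used at Visit 7 and at Early Termination covers the whole period since first treatment at Visit 3, and align Appendix 3 with it.
- Record the date of any positive answer.
- Flag pre-treatment events in the SAP 8.8 listing.

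This settles the recall period but gives no detection between doses. It also leaves the 6 to 10 weeks from screening to Visit 3 outside both forms.

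**Preferably**
- Also give the 'Since Last Visit' form at the existing in-clinic Visits 3 (before dosing), 4, 5 and 6. The Visit 3 form closes the pre-treatment interval, and the later ones assess the treatment period prospectively.

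If any Visit 7 forms have already been completed under the present wording, footnote the listing with the recall period the sites actually applied.

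**Cost**
- Either option changes the protocol and needs IRB approval (Protocol 12.1). That section lists added procedures meant to improve monitoring for an adverse event among the changes requiring an amendment submission.
- The four added administrations take about 4 × 5 = 20 minutes per participant, with no extra visits and using staff who must already be trained in the scale.
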